18.3.2.2 Early Stopping for Efficacy

For each histology, the combination therapy will be declared efficacious and enrollment terminated if a minimum of 10 subjects have response data available and the posterior probability that the ORR exceeds its corresponding historical control (C_j) is sufficiently high (>95%) based on the hierarchical model. That is,

$$P(\pi_j > C_j \mid \text{current data}) > 95\%, \text{ for the } j\text{-th histology.}$$

18.3.3 Final Analyses

The final primary analysis for ORR will occur once all subjects in the primary analysis cohort have either discontinued treatment or have received treatment for at least 8 months, whichever comes first. Secondary efficacy endpoints will likely not be mature at this time, but will still be reported. Subsequent analyses for secondary endpoints will occur at a date that would represent a minimum follow up of approximately 3 years for all subjects enrolled. These latter analyses will provide mature estimates/incidence for duration of response, PFS, OS, and safety.

18.3.3.1 Safety Analyses

Safety data will be presented in tabular and/or graphical format and summarized descriptively according to GSK' IDSL standards.

The ATS population will be used for the analysis of safety data. In general, safety data will be summarized by histology and across all cohorts

Complete details of the safety analyses will be provided in the RAP.

18.3.3.1.1 Adverse Events

Adverse events (AEs) will be coded using the standard MedDRA and grouped by system organ class. Adverse events (AEs) will be graded by the investigator according to the CTCAE, version 4.0.

Events will be summarized based on frequency and proportion of total subjects, by system organ class and preferred term. Separate summaries will be given for all AEs, treatment-related AEs, AEs by toxicity grade, SAEs and AEs leading to discontinuation of study treatment and dose modification.

Adverse events (AEs) of special interest will be identified and additional summaries provided.

The incidence of deaths and the primary cause of death will be summarized.

18.3.3.1.2 Clinical Laboratory Evaluations

Hematology and clinical chemistry data will be summarized by each scheduled assessment according to CTCAE, version 4.0, grade. The proportion of values lying outside the reference range will also be presented for laboratory tests that are not graded because there are no associated CTCAE grading criteria. Summaries will include data from scheduled assessments only, and all data will be reported according to the nominal visit date for which it was recorded (i.e., no visit windows will be applied). Unscheduled data will be included in “overall” and “any post-screening” summaries which will capture a worst case across all scheduled and unscheduled visits post first dose of study treatment.

18.3.3.1.3 Other Safety Measures

The results of scheduled assessments of vital signs, 12-lead ECG, ECHO and ECOG performance status will be summarized. Summaries will include data from scheduled assessments only. All data will be reported according to the nominal visit date for which it was recorded; no visit windows will be applied. All data will be listed.

18.3.3.2 Efficacy Analyses

ORR will be analyzed using an integrated analysis with the hierarchical model as well as analyzed independently **for each histology**.

At the final analysis a histology will be declared active if the posterior probability that the ORR exceeds its corresponding historical control (10%) is sufficiently high (>92%) based on the hierarchical model. That is,

$$P(\pi_j > C_j \% \mid \text{current data}) > 92\%, \text{ for the } j\text{-th histology.}$$

The observed ORR and the estimated ORR based on the hierarchical model will be reported for each histology. Confirmed ORR will be calculated as the proportion of subjects that have a confirmed response relative to the total number of subjects enrolled. Standard response assessments vary by histology; the following subcategories for each histology will be considered a ‘response’ to therapy when computing confirmed ORR.

Table 31 Response Subcategories Defined as ‘Response’ by Histology

Histology	Response Criteria	Response Subcategories defined as ‘Response’
ATC, BTC, GIST, Small Intestine Adenocarcinoma	RECIST 1.1	CR, PR
NSGCT/NGGCT	RECIST 1.1. Tumor Markers: β -HCG and AFP	Marker-Negative CR, Marker-Positive CR, Marker-Negative PR, Marker-Positive PR
MM	IMWG Uniform Response Criteria for MM	sCR, CR, PR, VGPR
HCL	Adapted from NCCN guidelines, Consensus Resolution Criteria and previous studies definition	CR \pm MRD, PR
WHO Grade 1 and 2 Gliomas	Response Assessment Criteria for WHO Grade 1 or 2 Gliomas: RANO Working Group	CR, PR, MR
WHO Grade 3 and 4 Gliomas	Updated Response Assessment Criteria for WHO Grade 3 or 4 Gliomas: RANO Working Group	CR, PR
Abbreviations: AFP, alpha-fetoprotein; ATC, anaplastic thyroid cancer; β -hCG, beta-human chorionic gonadotropin; BTC, biliary tract cancer; CR, complete response; GIST, gastrointestinal stromal tumor; HCL, hairy cell leukemia; IMWG, International Myeloma Working Group; MM, multiple myeloma; MR, minor response;		

NCCN, National Comprehensive Cancer Network; NGGCT, non-geminomatous germ cell tumor; NSGCT, non-seminomatous germ cell tumor; PR, partial response; RANO, Response Assessment for Neuro-Oncology; RECIST, Response Evaluation Criteria in Solid Tumors; sCR, stringent complete response; VGPR, very good partial response; WHO, World Health Organization

Further details on response confirmation criteria for each histological cohort will be provided in the RAP. Subjects with unknown or missing response will be treated as non-responders; that is, they will be included in the denominator when calculating the percentage.

The observed confirmed ORR will be reported at the final analysis for each histology. The estimates along with 95% exact confidence interval (CI) will be provided.

Bayesian inference based on summary statistics from the posterior distributions of each ORR will be reported. The posterior mean and posterior 2.5% and 97.5% percentiles of the ORR will be calculated for each histology. In addition, the posterior probability that the ORR exceeds its corresponding historical control will be reported for each histology.

Duration of response for the subset of subjects who have a confirmed response (See [Table 31](#)) is defined as the time from first documented evidence of response until the first documented sign of disease progression or death. Duration of response will be summarized descriptively for each histology, if data warrant, using Kaplan-Meier medians and quartiles. Details on rules for censoring will be provided in the RAP.

Progression-free survival (PFS) is defined as the time from the date of enrollment to the earliest date of progression or death. Progression-free survival (PFS) will be summarized by histology, if data warrant, using Kaplan-Meier quartile estimates along with 2-sided 95% CIs. If the subject does not have a documented date of progression or death, PFS will be censored at the date of the last adequate assessment. Further details on rules for censoring will be provided in the RAP. Progression-free survival (PFS) will be reported at the time of final primary analysis for overall response rate (ORR), regardless of the maturity of the data, and then updated at the final analysis.

Overall Survival (OS) is defined as the time from the date of enrollment to the date of death due to any cause. Censoring will be performed using the date of last known contact for those who are alive at the time of analysis. Overall survival (OS) will be summarized by histology, if data warrant, at the time of final primary analysis for overall response rate (ORR), regardless of the maturity of the survival data, and then updated at the final analysis.

Further details including possible sensitivity analyses will be provided in the RAP.

[REDACTED]

[REDACTED]

[REDACTED]

[REDACTED]

should not have a significant impact on operating characteristics of the design. Simulations assumed interim analyses occurred every 12 weeks, with the first interim analysis occurring once 10 subjects have been enrolled. The time from subject entry until the response assessment was performed is assumed to be 8 weeks. The maximum length of time for each study is 156 weeks \pm 6 weeks (roughly 3 years).

Although actual enrollment may vary, predicted enrollment during a 3-year time period is incorporated into the simulations. Because enrollment varies by histology, a numbering scheme (1 through 9) is used in simulations and corresponding results to index the nine histologies. Histology indexing, projected enrollments and the historical control and clinically meaningful response rates used in simulations are shown in Table 32.

Table 32 Projected Enrollment and Indexing by Histology

Histology	Histology Index	Projected enrollment in a 3-year time period				Historical Control/ Clinically Meaningful RRs
		Case 1	Case 2	Case 3	Case 4	
ATC	3	10	20	25	25	15% / 60%
BTC	2	10	16	16	10	10% / 50%
GIST	7	5	5	5	2	10% / 50%
HCL	1	15	17	20	20	10% / 50%
WHO Grade 1 or 2 Glioma	6	5	8	8	5	10% / 50%
WHO Grade 3 or 4 Glioma (high-grade)	5	5	16	16	8	10% / 50%
MM	8	5	17	20	20	15% / 60%
NSGCT/NGGCT	9	5	5	5	2	25% / 75%
ASI	4	8	5	5	2	10% / 50%

Abbreviations: ASI, adenocarcinoma of small intestine; ATC, anaplastic thyroid cancer; BTC, biliary tract cancer; GIST, gastrointestinal stromal tumor; HCL, hairy cell leukemia; MM, multiple myeloma; NGGCT, non-geminomatous germ cell tumor; NSGCT, non-seminomatous germ cell tumor; RR, response rate; WHO, World Health Organization

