18 DATA ANALYSIS AND STATISTICAL CONSIDERATIONS

18.1 Hypotheses and Treatment Comparisons

Subjects with rare BRAF V600E mutation-positive cancers will be enrolled, with the primary objective of evaluating clinical activity according to ORR. Response assessment for most solid tumors (ATC, BTC, GIST, NGGCT/NSGCT and adenocarcinoma of small intestine) will be evaluated by RECIST version 1.1 while all other tumors (HCL, MM and WHO Grade 1 or 2 glioma or WHO Grade 3 or 4 glioma) will use the appropriate established response criteria.

To further investigate clinical activity and compensate for the small sample sizes across the histologies, an adaptive design utilizing a Bayesian hierarchical model will be employed. Multiple interim evaluations of the accumulating data to determine if one or more histologic cohorts should discontinue enrollment early due to either success or futility will be incorporated. Interim and final evaluations will be based on a hierarchical model that borrows information in a limited way from histologies that demonstrate similar treatment effects based on the accumulated trial data. Traditional estimates based on independent analyses will also be provided.

π_j is the true response rate for histology j , where $j = 1, \dots, 9$ and indexes the nine histologies. C_j is the historical control response rate for the j th histology. The historical controls vary by histology and are provided in Table 29. The study is powered to detect a high clinically meaningful response rate and is based on the hierarchical model assessment of whether there is sufficiently high probability that π_j exceeds C_j . The posterior probability that the ORR for a given histology is greater than C_j will be computed according to the following comparison:

$$P(\pi_j > C_j \mid \text{current data}) \text{ for the } j\text{-th histology}$$

If this posterior probability is sufficiently low within a given histology, then this will provide insufficient evidence to suggest that the ORR is greater than its respective historical control. Conversely, if a sufficiently high posterior probability is observed, this will provide evidence that the ORR is greater than the historical control, and the combination arm will be declared efficacious in that histology. Thresholds for decision-making are defined in Section 18.3.

Historical control and clinically meaningful response rate varies by histology and is provided in Table 29.

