18.4.2 Operating Characteristics

18.4.2.1 Power and Type I Error Rate

[figure not shown]
Power and type I error rate are examined across scenarios for the distribution of assumed true ORRs for each histology. The power is the probability of declaring efficacy within a histology when the true underlying ORR is greater than its corresponding historical control. Type 1 error rate is the probability of declaring efficacy within a histology when the true underlying response rate is equal to the historical control. [Figure 1](#) illustrates the proportion of trials that declare each histology efficacious at the final analysis across simulation scenarios. Supporting tables for the simulation results are provided in [Appendix 7](#).

The power and type I error rate are dependent upon the sample sizes and response rates across the distribution of histologies. When the treatment effects are the same across all histologies (either all responsive or all non-responsive), estimation efficiencies, due to borrowing, result in very good operating characteristics, even in histologies with very low sample sizes. Under sample size Case 1, the type I error rate is controlled to ≤ 0.04 across all histologies (All Null scenario). The design maintains power 93% to 98% for the higher enrolling cohorts, and 84%

to 90% for the smallest enrolling 5 cohorts (All Great scenario). Also, the design exhibits reasonable power to detect a moderate level of activity (All moderate scenarios).

When the treatment effects vary across histologies, the amount of appropriate borrowing also varies, impacting the operating characteristics. The ‘2 Greats: Mixed’ investigates design performance where most histologies are not responsive. In this situation, the type I error rate is controlled to ≤ 0.06 and the power is 82% for the higher enrolling cohort and 55% for the low enrolling cohort. The ‘5 Greats: Mixed’, ‘5 Greats: Low’ and ‘Mixed’ scenarios investigate the design performance in situations where roughly half the histologies are responsive. The type I error rate ranges from 0.09 to 0.14 while the power ranges from 93% to 96% for the higher enrolling cohorts and ranges from 67% to 84% for the lower enrolling cohorts. Generally, improvement in the overall distribution of treatment effects tends to coincide with slight increases in type I error rate and moderate increases in power.

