Figure 1 Proportion of Studies that Declare each Histology Efficacious at the Final Analysis under Sample Size Case 1

18.4.2.2 Probability that the Model Declares Success Across Different Sample Sizes and Numbers of Observed Responses

No pre-determined number of responses or response rate will necessarily dictate model success or model failure. In addition to a particular histology response data, their corresponding historical control response rate and the overall distribution of treatment effects across the histologies impacts the model decision in that particular histology. To further understand the likelihood of model success, for each possible combination of sample size (≤ 15) and number of observed responses, the proportion of times the model declares such data efficacious at the final analysis is assessed by scenario but combining across histologic cohorts with the same historical control response rate. Hence, the likelihood of declaring success is explored for histologies with historical control response rates of 0.10 (histologies 1, 2, 4, 5, 6, and 7), 0.15 (histologies 3 and 8), and 0.25 (histology 9). Actual histologies, their simulation indexing number, and the appropriate historical control response rates are in [Table 29](#) in Section 18.4.1.3.

Figure 1 illustrate the proportion of trials that declare success across all possible combinations of sample sizes and number of observed responses and for each historical control response rate. Figure 2 illustrates a subset of this data, more clearly describing the probability of declaring success when 1, 2, 3, or 4 responses are observed.

Supporting tables for these simulation results are provided in Appendix 7. Some variability is expected in these estimates due to low sample sizes in some of these observed data combinations.

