2.4.2 Statistical hypothesis, model, and method of analysis

Confirmed ORR will be calculated as the proportion of subjects that have a confirmed response relative to the total number of subjects in the corresponding analysis population.

Confirmed ORR will be analyzed using an integrated analysis across the histologic cohorts with the hierarchical model. Model-based interim decision rules have been used through the study to identify whether one or more histologic cohorts halt enrolment early for futility/harm or benefit based on efficacy data.

Model-based decision rules for the final analysis are provided in the protocol. At the final analysis, a minimum of 2 subjects will be required in a histologic cohort in order to meet statistical success. A histologic cohort will be declared active if the posterior probability that the ORR exceeds its corresponding historical control is sufficiently high (>92%) based on the hierarchical model. That is,

$$P(\pi_j > C_j \% \mid \text{current data}) > 92\%, \text{ for the } j\text{-th histology.}$$

This decision rule has been determined based on extensive simulations of the study design as described in the protocol.

A summary of the Bayesian hierarchical model-based analysis will be provided. For each histology the following measures will be reported: the total number of subjects, the protocol-specified historical control response rate, the estimated response rate and 95% credible interval (based on the posterior mean and 2.5% and 97.5% percentiles), and the posterior probability that the ORR exceeds its corresponding historical control response rate.

Descriptive summaries of best confirmed response along with the corresponding 95% exact confidence intervals will be provided for each response criteria for the varying histologic cohorts in order to characterize the observed response data and support the model-based analyses for ORR. Best response and ORR will be presented for the primary cohort, expansion cohort and primary and expansion combined for each histology for which an expansion cohort was opened.

The model-based analysis of ORR and supporting summaries of best confirmed response will be re-produced based on the BRAF V600E Population.

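### The bracketed 10% in the protocol's final success rule contradicts the C_j formula beneath it and Table 29 for ATC, MM and NSGCT/NGGCT, and should be replaced by a reference to that table

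*Protocol*

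**What the plan says.** Protocol 18.3.3.2 gives the final rule for the primary endpoint. In words, the posterior probability that the ORR "exceeds its corresponding historical control (10"%) must be such that it "is sufficiently high (>92%) based on the hierarchical model". The next line writes the same rule as P(π_j > C_j | current data) > 92% for the j-th histology.

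Protocol 18.1 defines C_j as the historical control of histology j and adds: "The historical controls vary by histology and are provided in Table 29". Table 29 gives 15% for ATC and MM, 25% for NSGCT/NGGCT and 10% for the other six; Table 32 repeats these values. Section 18.4.2.2 groups the simulated cohorts by control rate, with 0.10 for six of them and "0.15 (histologies 3 and 8), and 0.25 (histology 9"); in Table 32 these indices are ATC, MM and NSGCT/NGGCT. The interim rules in 18.3.2.1 and 18.3.2.2 are written with C_j.

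SAP 2.4.2 first says: "Model-based decision rules for the final analysis are provided in the protocol". It then restates the rule: the posterior probability that the ORR "exceeds its corresponding historical control is sufficiently high (>92%) based on the hierarchical model", followed by the C_j formula and with no 10%. SAP section 3 declares no change from the protocol.

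**The concern.** This sentence sets the success threshold for the primary endpoint. Read with Table 29, the protocol carries two control values for ATC, MM and NSGCT/NGGCT. The SAP sends the reader to the protocol for the rule and prints no C_j values of its own, so the conflict has to be settled from the protocol.

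A lower control makes success easier. The error rates in 18.4.2.1 and Appendix 7 were simulated with histology-specific controls and describe only that rule. SAP 4.11 makes no multiplicity adjustment, so these simulated per-cohort rates are the error control the design offers. A cohort judged against 10% when its control is 15% or 25% would not have them.

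**Working it through.** **Inputs.** Controls from Table 29; final cut 0.92 (18.3.3.2); interim stops below 0.30 from 5 subjects and above 0.95 from 10 subjects, both against C_j (18.3.2.1, 18.3.2.2); interims every 12 weeks, 8-week response lag, 156 weeks and projected enrollment (18.4.1.2, Table 32); the clustered model of Appendix 6 with α = 2, τ² ~ IG(3, 0.5) and μ ~ N(0, 3).

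**Assumptions.** The 3 is a variance; the reference rate η_j in Appendix 6 is C_j; accrual is Poisson with the projected mean, capped at 25 per cohort.

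**Step 1: reproduce the plan's figures.** The model was summed exactly over all partitions of the nine histologies, and 1,000 trials were simulated per scenario.
- Appendix 8: all 54 final posterior probabilities (6 examples × 9 cohorts) are recovered, with mean absolute error 0.007 and largest 0.026.
- All-null Case 1: the protocol says "the type I error rate is controlled to ≤ 0.04 across all histologies (All Null scenario"). The rebuilt design gives 0.009 to 0.031.
- All-alternative Case 1 power: 92–98% for histologies 1–4 and 85–89% for 5–9, against a stated 93–98% and 84–90%.
- Appendix 7, Case 2, 2 Greats: Mixed1: MM 0.066 (stated 0.07), NSGCT/NGGCT 0.046 (stated 0.04).

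**Step 2: change only the final cut to 10%.** Same simulated trials, with interim stops left at C_j. True rates equal C_j in every cell below.

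| Setting | Cohort | Cut at C_j | Cut at 10% | Ratio |
|---|---|---|---|---|
| Case 1, all null | ATC | 0.027 | 0.115 | 4.3 |
| | MM | 0.022 | 0.078 | 3.5 |
| | NSGCT/NGGCT | 0.023 | 0.325 | 14 |
| Case 1, 2 Greats | ATC | 0.049 | 0.152 | 3.1 |
| | MM | 0.045 | 0.113 | 2.5 |
| | NSGCT/NGGCT | 0.063 | 0.385 | 6.1 |
| Case 2, 2 Greats: Mixed1 | MM | 0.066 | 0.182 | 2.8 |
| | NSGCT/NGGCT | 0.046 | 0.362 | 7.9 |
| Case 2, 4 Greats: Low | ATC | 0.097 | 0.229 | 2.4 |
| | MM | 0.080 | 0.201 | 2.5 |
| Case 2, 5 Greats: Mixed1 | MM | 0.108 | 0.216 | 2.0 |

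If 10% also replaced C_j as the reference rate inside the model, the all-null Case 1 values would be 0.085, 0.056 and 0.158 (ratios 3.1, 2.5 and 6.9). Monte Carlo standard error is about 0.005 at 0.03 and 0.015 at 0.33.

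**Step 3: a check without the model.** With a flat prior and no borrowing, P(π > c | y of n) = P(Bin(n+1, c) ≤ y). For NSGCT/NGGCT with n = 5 and c = 25%, y = 2 gives 0.831 and y = 3 gives 0.962, so success needs 3 responses. With c = 10%, y = 1 gives 0.886 and y = 2 gives 0.984, so 2 suffice. At a true rate of 25%, P(Y ≥ 3) = 0.104 and P(Y ≥ 2) = 0.367. For n = 25 at a true 15%, the bar falls from 7 responses to 5 and the rate rises from 0.070 to 0.318. These fixed-size figures show direction only; they are not error rates of the design.

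**Step 4: the protocol's own examples.** NSGCT/NGGCT is printed as futility in Example 1 (1/3, probability 0.88) and Example 3 (2/7, 0.77). Against 10% both become 0.97, or 0.96 with 10% also inside the model: success either way. In Example 2 (2/3, printed 0.77) the value is 0.98 with the cut alone and about 0.92, at the boundary, with both changed. No ATC or MM decision in the six examples changes.

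**The case against.** The strongest reply is that the rule itself is not in doubt. The formula follows the sentence immediately and uses C_j. The phrase about a control corresponding to the histology makes little sense with one common value. Protocol section 4, 18.1, both interim rules, Tables 29 and 32, 18.4.2.2, all six worked examples and the SAP's restatement are histology-specific. All of that stands, and it makes leftover text the likely explanation.

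A reader might infer something stronger: that the governing rule tests every histology against 10%, so that the trial runs at several times its stated error rates. The documents do not support this. An analyst would have to prefer the bracket to the formula, the tables, the examples and SAP 2.4.2.

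Two further limits are fair. The protocol already states type I error up to 0.14 in mixed Case 1 scenarios and up to 0.18 with larger cohorts, so comparisons must be made within a scenario. And the largest ratio falls on NSGCT/NGGCT, which SAP 2.6 does not list for secondary efficacy analysis.

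None of this makes the bracketed figure correct for three cohorts. It stands in current text, in a primary-endpoint decision rule.

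**Conclusion.** The bracketed 10% is an internal contradiction to be corrected; it is not evidence that the wrong threshold will be used. Six cohorts are unaffected because their C_j is 10%.

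The consequence is conditional. If 10% were applied as the final cut, all-null Case 1 error would be 0.078 to 0.325 in the three affected cohorts, against a stated ceiling of 0.04. The ratio to the C_j rule would be about 2 to 4 for ATC and MM (about 2 to 3 in mixed baskets) and about 6 to 14 for NSGCT/NGGCT, lower if 10% also entered the model.

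These sizes rest on the assumed accrual process and on the readings of Appendix 6 given above. Agreement with Appendix 7 is not perfect: Case 3, 4 Greats: Low gives ATC 0.115 against 0.09, and Case 2, 5 Greats: Mixed1 gives ASI power 0.73 against 0.82. Because both cuts were applied to the same simulated trials, this does not affect the comparison.

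**What to change.** In Protocol 18.3.3.2, replace the bracketed 10% with: C_j as given in Table 29. Printing the values (10%, 15% or 25%) beside the rule in SAP 2.4.2 would help the programmer but is optional, since the SAP formula already uses C_j. The cost is wording only; no design, data, simulation or analysis changes.
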